1. INTRODUCTION

This is an adaptive Phase 1b/2 study with three parts, the sentinel phase which is an open label, dose escalation of approximately 6 patients with Type 1 diabetes (T1DM) on CSII and CGM (sentinels) with up to 8 visits, Part 1 with approximately 30 randomized patients with type 1 diabetes on CSII dosing for 12 weeks with up to 10 visits and Part 2 with approximately 90 randomized patients with type 1 diabetes on CSII or MDI with up to 9 visits. The analysis of the sentinel phase suggested positive results [as defined in Section 3.4 (Rationale for progression)], resulting in Part 1 being initiated. Part 2 will be initiated following positive results from an interim analysis of Part 1 [See Section 3.4.2 Rationale for progression into Part 2]. Completion of Parts 1 and 2 will result in approximately 120 patients dosing for 12 weeks. Each part of the study will have a screening period, a baseline period, an open label dose escalation phase (Sentinels Phase only) and a double-blind, placebo-controlled treatment period (Part 1 and 2, randomized 1:1 to placebo or TTP399). Part 1 and Part 2 will have an insulin dose adjustment period, if needed. Sentinel and Part 1 patients will have unblinded CGM the entire study and will be contacted by the site daily to assess safety. In Part 2 there will be two periods of sponsor provided (blinded) CGM. In addition to site visits, patients will be contacted throughout the study to assess safety as outlined in the Schedule of Activities. Phone calls are preferred, but texts are allowed.. Mixed meal tolerance test (MMTT) will be conducted in the Sentinel patients. Pharmacokinetic samples will be collected throughout the study for all patients. A planned interim analysis may occur approximately 6 weeks after approximately 30 patients have been randomized in Part 1.

1.1. Background and Rationale

While multiple oral drugs are approved for the management of hyperglycemia in type 2 diabetes (T2DM), no oral therapies are approved that improve hyperglycemia in type 1 diabetes (T1DM). There is an unmet medical need to provide people with type 1 diabetes treatment options that help them to achieve tighter blood glucose levels and reduce insulin doses without increasing the risk of hypoglycemia or ketoacidosis.

1.1.1. Type 1 Diabetes Mellitus

Type 1 diabetes (T1D) is an autoimmune disease that usually leads to absolute insulin deficiency. Multiple genetic predispositions and poorly defined environmental factors result in the autoimmune destruction of pancreatic β -cells, the site of insulin secretion¹. T1D affects more than one million people in the United States and strikes both children and adults at any age. Most T1D patients are on insulin therapy (multiple daily injection of prandial insulin and basal insulin or continuous subcutaneous insulin infusion) to control their blood sugar, however, there is significant unmet need as maintaining proper glycemic control with insulin therapy is demanding on patients and comes with significant risk of hypoglycemia that can have serious cognitive effects as well as long term complications affecting multiple organs. Improvements in the delivery of insulin have been made recently to reduce the risk of hypoglycemia, but reduction of required insulin doses and/or increasing time in glycemic range using oral anti-diabetic therapies acting through different mechanisms could meet a significant unmet need for Type 1 diabetic patients.

1.1.2. Mechanism of Action

TTP399 is a liver-selective glucokinase activator. Glucokinase (GK), plays an essential role in blood glucose homeostasis. It catalyzes glucose phosphorylation and is the rate-limiting reaction for glycolysis². In the liver, GK determine the rates of both glucose uptake and glycogen synthesis (Figure 1), and it is also thought to be essential for the regulation of various glucose-responsive genes^{3,4}. Data from transgenic animals in which only liver glucokinase has been up regulated by different mechanisms clearly shows that a selective increase in hepatic glucokinase is the only requirement for the normalization of the metabolic profile in insulin deficient animals. These observations suggest that selective activation of liver GK could provide a mechanism that ensures reduction of blood glucose without the risk of hypoglycemia

[figure not shown]

Figure 1: Schematic representation of the role of GK in the liver

1.1.3. Nonclinical Studies

Animal models have confirmed that liver-selective GK activator TTP399 significantly improves glycemic control, reduce insulin resistance, and decrease body weight without changes in β -cell mass, plasma insulin, or hepatic lipids.

The toxicokinetic data from the 9-month oral toxicity study in minipigs demonstrated approximate safety margins of 37-fold and 32-fold for AUC₀₋₂₄ and C_{max} for the dose of 1600mg/day (800mg BID).

Refer to the IB for additional information on the non-clinical pharmacology and toxicology.

A pilot study in a model of type 1 diabetes, where following streptozotocin administration, beta-cell reduced Gottingen minipigs dosed with a liver-selective GKA with identical pharmacological properties to TTP399 provided preclinical evidence supporting the concept of liver-selective GKAs for the treatment of T1DM. Treatment with the liver selective GKA reduced by half the dose of exogenous insulin needed to maintain glycemic control in this type 1 model of minipigs. Dosing with the liver-selective GKA was well tolerated and no hypoglycemia was seen in the animals even when insulin was dosed in the absence of food.

In addition, during a 4-day period without insulin administration, treatment delayed/prevented increase in glucose and ketone bodies, reduced glucagon and maintained buffer capacity in blood.

1.1.4. Clinical Studies

Results from the preclinical program supported the initiation of 9 Phase 1 trials and 2 Phase 2 trials of TTP399. These eleven trials have evaluated 701 patients; 494 of whom received one or more doses of TTP399 (182 healthy subjects and 312 patients with T2DM). Nine of these studies were Phase 1 trials studies (up to 10 days of dosing) conducted in healthy volunteers or patients with T2DM. Two Phase 2 trials have been conducted, a Phase 2a study involving 6 weeks of dosing in patients with T2DM and a 6-month Phase 2b study in patients with T2DM on stable doses of metformin. In these studies, the incidence of adverse events was similar for healthy and T2DM patients administered TTP399 compared to placebo. There were no AEs that had an obvious treatment-related relationship to dose, no concern of hypoglycemia associated with TTP399 treatment, and no demonstrated adverse effects of TTP399 on vital signs, ECG parameters, or clinical laboratory assessments. Current studies have not revealed a maximum tolerated dose with single doses up to 1200 mg and multiple doses up to 800 mg BID being well tolerated.

In clinical studies evaluating T2DM patients, TTP399 has shown significant reductions in postprandial glucose, increasing % time in range and decreasing % time of hypo or hyperglycemia. In the 6-month Phase 2b clinical trial in type 2 diabetic patients on stable doses of metformin, TTP399 significantly reduced A1c and the effect was sustained for the duration of the study without significant hypoglycemia, dyslipidemia or ketoacidosis.

Refer to the IB for additional information on clinical results.

2. STUDY OBJECTIVES AND ENDPOINTS

2.1. Sentinel phase

Objectives

The **primary objectives** of this study are:

- To investigate the pharmacokinetic (PK) profiles of the tablet formulation of TTP399 in patients with type 1 diabetes mellitus (T1DM) with continuous subcutaneous insulin infusion (CSII) and continuous glucose monitoring (CGM)
- To assess the safety and tolerability of TTP399 following 7 days of repeated dosing at up to 3 doses.

The **secondary objective** of this part of the study is:

- To evaluate the pharmacodynamic (PD) effect of TTP399 following multiple dosing (up to 7 days at up to 3 doses) in patients with T1DM to determine optimal efficacious dose to improve glycemic control and/or reduce mealtime

insulin bolus

Outcome Measures

Primary Outcome Measures:

- Pharmacokinetic Measures: Cmax, Tmax, and AUC(0- τ), t1/2
- Adverse events, clinically significant changes from baseline in laboratory tests, vital signs and electrocardiograms (ECG) parameters

Secondary Outcome Measures:

- Change from baseline MMTT AUC 0-3h glucose
- Change from baseline in bolus insulin (number of units and / or number of bolus injections) for the last 3 days in each 7 day interval
- Percent change from baseline in bolus insulin for the last 3 days in each 7 day interval
- Change from baseline total daily insulin for the last 3 days in each 7 day interval
- Percent change from baseline total daily insulin for the last 3 days in each 7 day interval
- Change from baseline in average daily glucose for the last 3 days in each 7 day interval
- Percent time in target glycemic range (70-180 mg/dL); hyperglycemic range (Level 1 > 180 mg/dL; Level 2 >250mg/dL) and hypoglycemic range (Level 1 < 70mg/dL; Level 2 < 54 mg/dL)
- Percent time in target glycemic range of 70-140mg/dL during the last 3 days in each 7 day interval
- Mean post prandial (0-3hr) glucose during the last 3 days in each 7 day interval
- Hypoglycemic events by CGM (\geq 15 continuous minutes of glucose reading <70mg/dL)
- Glycemic variability (mean SD and CoV)
- Change from baseline of non-genomic biomarkers, glucagon and GLP-1
- Body weight

2.3. Parts 1 and 2 (Following 12 weeks of dosing)

Objectives

Primary Objective:

- To evaluate the pharmacodynamic (PD) effect of TTP399 following multiple day dosing (at 12 weeks) in patients with T1DM

Secondary Objectives:

- To evaluate the safety and tolerability of TTP399 administered for 12 weeks in T1DM patients

Exploratory Objectives

- Assess relevancy of non-genomic biomarkers in predicitng responders and efficacy
- To assess changes in patient quality of life

Endpoints (Part 1 and Part 2)

Primary Endpoint:

- Change from baseline in HbA1c at 12 weeks

Secondary Endpoints:

- Change from baseline time in target glycemic range (70-180 mg/dL); hyperglycemic range (Level 1 > 180 mg/dL; Level 2 (>250mg/dL) and hypoglycemic range (Level 1 < 70mg/dL; Level 2 < 54 mg/dL)
- Change from baseline in number of units of insulin (basal, bolus or total daily) dose
- Percent change from baseline in insulin (basal, bolus or total daily) dose
- Achievement of a decrease of at least 0.3% in HbA1c at Week 12 (responders)

Safety Endpoints:

- Adverse events, laboratory, vital sign and electrocardiograms (ECG) parameters

Exploratory Endpoints:

- Plasma (non-genomic) biomarkers
- Diabetes treatment satisfaction questionnaire (s)
- Change from baseline in number of bolus injections of insulin
- An analysis of responders HbA1c < 7% without any severe hypoglycemic events, weight gain, ketoacidosis

Endpoints (Part 1, Interim analysis):

An interim analysis plan that will describe the variables of analysis. Endpoints will include, but not be limited to the following:

Primary Endpoints:

- Change from baseline in bolus insulin (number of units) OR
Change from baseline for time in target glycemic range (70-180 mg/dL)

Secondary Endpoints:

- Change from baseline for time in hyperglycemic range (Level 1 > 180 mg/dL; Level 2 (>250mg/dL) and hypoglycemic range (Level 1 < 70mg/dL; Level 2 < 54 mg/dL)
- Composite endpoint encompassing change from baseline HbA1c and risk of hypoglycemia as described in the SAP
- Change from baseline in average daily glucose

Safety Endpoints:

- Adverse events, laboratory, vital sign and electrocardiograms (ECG) parameters

Exploratory Endpoints:

- Change from baseline in basal or total daily insulin dose (number of units)
- Percent change from baseline in insulin (basal, bolus or total daily) dose
- Change from baseline glycemic markers (fructosamine and 1,5 anhydroglucitol)
- Body weight
- Glycemic variability (mean SD and CoV)
- Change from baseline total daily insulin dose
- Percent change from baseline in total daily insulin

3. ADAPTIVE STUDY DESIGN AND RATIONALE:

This adaptive study to evaluate TTP399 as a potential treatment for T1DM will occur in three parts (sentinels, learning phase (Part 1) and confirming phase (Part 2)) with the opportunity to modify the study. Weekly dose escalations (anticipated from 400mg to 1200 mg daily doses of TTP399) will occur in up to 6 sentinel patients on CSII and CGM (open label) to determine the dose to be compared with placebo in approximately 120 Type 1 diabetes patients using either CSII or MDI (with a goal of approximately 30 patients in Part 1 and approximately 90 patients in Part 2). Some possible adaptations envisioned include dose regimen, endpoints and number of patients randomized into Part 1 and 2. The study population will consist of patients with T1DM who have experience using either CSII or MDI. Patients will be dosed daily with TTP399 (orally) or placebo during the treatment period. Continuous Glucose Monitoring will be used to monitor safety and efficacy and mixed meal tolerance tests will be conducted in sentinel patients. Pharmacokinetic samples will also be obtained.

The three parts of this an adaptive Phase 1b/2 study are:

[figure not shown]
- Sentinel phase: an open label, dose escalation with approximately 6 adult T1DM patients (sentinels) with up to 8 visits,
- Part 1: a placebo-controlled study with approximately 30 randomized adult type 1 diabetic patients dosing for 12 weeks with up to 10 visits and
- Part 2: a placebo-controlled study with approximately 90 total randomized adult type 1 diabetic patients with up to 9 visits.

The analysis of the sentinel phase suggested positive results based on our progression rationale (Section 3.4.1), so Part 1 was initiated. Part 2 will be initiated upon completion of approximately 50% of patients in Part 1 in the absence of safety concerns resulting from ongoing safety review of accruing data. Completion of Part 1 and 2 will result in approximately 120 patients dosing for 12 weeks. Consented patients who have met screening criteria when the enrollment goals are met will be allowed to continue until up to a total number of approximately 140 patients are enrolled in the study.

3.1. Sentinel phase

This will be conducted at only one site. The Sentinel phase of this adaptive Phase 1b/2 study is to evaluate the safety, pharmacokinetics and pharmacodynamics of different dose regimens ranging from 400 to 1200mg daily doses of TTP399 in adult Type 1 Diabetic patients. The study population for the sentinel phase of the study will consist of patients with T1DM who are currently be using CGM and CSII. This study will be initiated with 6 patients in an open-label, weekly dose escalation study with up to 3 dose escalations (7 days dosing at each dose level). Patients will be dosed initially with a once daily dose of TTP399 during the treatment period. Since this is an adaptive study, dosing regimens may be modified based on patient results with regards to dose amount (up to 1200 mg per day) and frequency (BID or other alternative dosing strategies). Study stopping criteria for the sentinel patients (outlined below) are based on safety and efficacy criteria. Unblinded Continuous Glucose Monitoring will be used to monitor safety and efficacy.

See [Figure 2](#) for a schematic of the study design and the [SCHEDULE OF ACTIVITIES \(SENTINELS\)](#) for the timing of study procedures.

Figure 2: Study Design: Sentinel Patients. Open label with dose escalation, 3 periods (7 days per period), no washout between periods; anticipated doses are listed, conducted at 1 site

3.1.1. Sentinel Phase Dose Escalation Stopping Rules

All patients in this study will be closely monitored for emergent signs or symptoms indicating possible adverse effects. Dose escalation stopping rules will be used to direct the safety committee to determine whether the maximum tolerated dose has been attained. The following is a list of dose escalation stopping rules. If dose escalation is stopped due to any of these findings, additional periods using different dosing regimens may be implemented.

3.1.1.1 Individual Patient Criteria

- If an individual patient experiences an episode of severe hypoglycemia [as defined in Section 9.8.2], the patient will be instructed to stop dosing, contact the site AND come to the site for follow-up safety visits as determined by the investigator. The patient will NOT be restarted on study drug unless there were substantial aggravating issues precipitating the episode as determined by the Investigator.
- If an individual patient experiences an episode of diabetic ketoacidosis DKA [as defined in Section 9.8.3], the patient will be instructed to stop dosing, contact the site AND come to the site for follow-up safety visits as determined by the investigator. The

patient will NOT be restarted on study drug unless there were substantial aggravating issues precipitating the episode as determined by the Investigator.

- If a patient post prandial glucose is maintained at less than 180mg/dL as determined by CGM in the absence of mealtime bolus insulin the dose given will be determined to be efficacious and only one more dose escalation for that patient will be conducted.

3.1.1.2 Dose Level Criteria

[figure not shown]
- Dose escalation will be stopped if two or more patients develop similar drug-related clinically significant laboratory, ECG or vital signs abnormalities, or dose-related severe AEs in the same organ class, indicating dose-limiting intolerance.
- Dosing will be paused for any serious adverse event (SAE) that occurs in a patient receiving active treatment until causality is fully assessed by the PI and Sponsor. Dosing will cease if the SAE was determined to be drug-related, and may resume if determined to be not drug-related by the PI and Sponsor.
- Dose escalation will be stopped if it is determined that the limits of safety and/or tolerability have been reached. This decision will be made after a discussion takes place between the vTv study team and the study site team.
- The sentinel study will be paused if 2 or more patients experience at least one episode of severe hypoglycemia [as defined in Section 9.8.2].
- The sentinel study will be paused if 2 or more patients experience at least one episode of DKA [as defined in Section 9.8.3].
- Other findings that, at the discretion of the Study Team and Investigator, indicate that dose escalation should be halted

3.2. Parts 1 and 2

3.2.1. Part 1

Part 1 is a multi-center (up to 5 sites) double-blind placebo-controlled study with a 2-week single-blind placebo run-in period to evaluate TTP399 as a potential adjunctive treatment to insulin therapy for T1DM. The study will examine the safety and pharmacodynamic response at 12 weeks of dosing in patients randomized (1:1) to either placebo or 800 mg QD TTP399. Part 1 will enroll approximately 30 adult type 1 diabetic patients who have experience using CSII and CGM. Approximately six weeks after 30 patients are randomized, a planned interim analysis will be conducted to evaluate safety and efficacy. Unblinded Continuous Glucose Monitoring will be used to monitor safety and efficacy throughout the study. See Figure 3 for a schematic of the study design and the SCHEDULE OF ACTIVITIES (PART 1) for the timing of study procedures.

Figure 3: Study Design: Part 1- Double blind placebo-controlled randomized (1:1) with up to 5 sites, n=approximately 30 patients, treatment period 12 weeks.

[figure not shown]
Stopping Criteria Part 1

- Part 1 will be paused if 3 or more patients experience at least one episode of severe hypoglycemia defined as **each** of the following criteria being met:
 - a) The patient was unable to treat him/herself, requiring the assistance of another person to actively administer carbohydrate, glucagon, or other resuscitative actions. Neurologic impairment must be the explanation for why the patient could not treat him/herself and required the assistance of another person.
 - b) Blood glucose:
 - If blood glucose was measured and was ≤ 49 mg/dL (2.7 mmol/L) using plasma referenced- home glucometers, CGM (or central laboratory), **or**
 - If blood glucose was not measured, the clinical manifestations were reversed by oral carbohydrates, subcutaneous glucagon, or intravenous glucose.
- Part 1 will be paused if 3 or more patients experience at least one episode of DKA [as defined by
 - a) Increased serum β - hydroxybutyrate or urine ketones (above ULN) **AND**
 - b) serum bicarbonate (total CO_2) < 15 mmol/L **OR** blood pH < 7.3

3.2.2. Part 2

Part 2 is a double-blind placebo control study to be conducted at up to 20 sites to evaluate TTP399 as a potential adjunct treatment for T1DM that will examine the safety, pharmacokinetic and pharmacodynamic response after 12 weeks of dosing in approximately 90 adult T1DM patients randomized (1:1) to either placebo or a dose of 800 mg QD TTP399. Since this is an adaptive study, modifications in the endpoints and/or the number of patients randomized to each treatment group in Part 2 may or may not occur based on information from the analysis of safety, PK and PD parameters in Part 1 or the Sentinels. The sponsor will provide Continuous Glucose Monitoring Devices (blinding) to be used at two timepoints during the study, including during baseline and at the end of the dosing period. Patients will be provided glucometers and glucometer related supplies to monitor glucose levels, if needed. See Figure 4 for a schematic of the study design and the [SCHEDULE OF ACTIVITIES \(PART 2\)](#) for the timing of study procedures.

Figure 4: Study Design: Part 2 - Double blind placebo-controlled randomized (1:1) with up to 20 sites, n=90 patients. Treatment period 12 weeks

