3.4. Study Progression Rationale

3.4.1. Rationale for progression into Part 1:

The sentinel phase results demonstrate that TTP399 once daily dosing up to 1200 mg QD was well tolerated in 5 patients with Type 1 Diabetes on insulin. No incidences of severe hypoglycemia or diabetic ketoacidosis occurred during this phase of the study. When compared to baseline, trends toward improved glycemic control while reducing insulin dose were observed with TTP399 treatment, providing support for the progression to the randomized, placebo control Part 1 of the study based on the following criteria outlined prior to study start:

- TTP399 is well tolerated;**

and one or more of the following:

- TTP399 treatment shows an improvement in one or more of the secondary outcomes, e.g. AUC 0-3hr, time in range, less hypoglycemia.**
- TTP399 maintains glycemic control while reducing insulin dose or simplifying**

insulin regimen

And successful IRB approval of any protocol changes based on the Sentinel phase and ICF approval, as applicable.

3.4.2. Rationale for progression into Part 2:

The results of the ongoing safety review of accruing data will advise whether the TTP399 program development can move forward. Part 2 will be initiated upon completion of approximately 50% of patients in Part 1 in the absence of safety concerns.

4. STUDY REQUIREMENTS AND RESTRICTIONS:**4.1. Meals and Dietary Restrictions**

For clinic visits to the site (beginning with the baseline CGM visit (Sentinels) and Week -2 (Part 1 and 2) and continuing through follow-up), patients will be instructed to arrive before their morning meal and before taking mealtime insulin and their study medications for that day, as applicable. Measures to mitigate hypoglycemia are allowed, e.g. glucose tablets.

Sentinel Patients:

For all clinic visits when MMTTs are conducted, the patients will be given lunch with a standardized carbohydrate content (between 30-100 g of carbohydrate). Each patient will select a lunch at the baseline MMTT visit [Day -7 for Sentinels]. The same lunch will be provided at all visits requiring MMTTs and be required to consume the entire meal.

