A sufficient number of study participants will be screened and admitted in order to randomize approximately 90 study participants into Part 2 from up to 20 sites. Patients who have met screening criteria when the enrollment goals are met will be enrolled until up to a total of approximately 140 patients enrolled in Part 1 and 2. The study population will consist of patients with T1DM who have experience using either CSII or MDI (Part 2). Patients enrolling in Part 2 are NOT required to have experience with CGM, however, patients enrolling in the study currently on personal CGM are required to have at least 2 months of experience with CGM without significant interruptions (i.e. > 2 weeks) prior to screening and agree to continue using their personal CGM throughout the study in addition to the sponsor provided CGM. If patients are not using personal CGM at screening, they should agree to not start any personal CGM during the study.

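### Part 2 has no study-level pause count for severe hypoglycemia or DKA, although the Protocol sets one for the Sentinels and for Part 1

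*Protocol*

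**What the plan says.** Protocol 3.1.1.2 gives the Sentinels two study-level rules: "The sentinel study will be paused if 2 or more patients experience at least one episode of severe hypoglycemia", and "The sentinel study will be paused if 2 or more patients experience at least one episode of DKA". Protocol 3.2.1, under its Part 1 stopping criteria, has "Part 1 will be paused if 3 or more patients experience at least one episode of severe hypoglycemia defined as" a two-part definition, and "Part 1 will be paused if 3 or more patients experience at least one episode of DKA". Both sets of counts are in the Protocol; the SAP sets no pause count for any part.

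Protocol 3.2.2 describes Part 2 ("Part 2 is a double-blind placebo control study to be conducted at up to 20 sites") and has no stopping criteria. The provisions that do reach Part 2 are:

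- **Entry gate (3.4.2):** "Part 2 will be initiated upon completion of approximately 50% of patients in Part 1 in the absence of safety concerns". This controls whether Part 2 opens, not what happens afterwards.
- **Single patient (9.8.2):** treatment stops after severe hypoglycemia if the investigator judges the episode both unexpected and unavoidable in future. Section 9.8.3 has no matching rule for DKA.
- **Case review (9.8.2, 9.8.3, 10.9):** an independent data monitor evaluates severe hypoglycemia and adjudicates DKA; a contracted, possibly unblinded endocrinologist evaluates SAEs and events of special concern.
- **Reporting (9.5.3, 9.7.1):** SAEs go to the sponsor within 24 hours, and SAEs and SUSARs go to the IRB.
- **Periodic review (10.7, 10.9; SAP 6.2, 7.7.2):** ongoing review, blinded sponsor review about monthly, and medical monitoring aimed at both events.
- **Board (10.9):** an ad hoc safety board is optional.
- **Termination (14):** a right that the sponsor reserves.

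SAP 1.10 names early stopping in its title, but its text covers only optional interim analyses.

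**The concern.** The Protocol treats both events as being of special concern. In Part 1, three affected patients lead to a pause by rule. In Part 2, which has three times the patients (90 against 30) and up to four times the sites (20 against 5), the same cluster leads to a pause only if someone decides on one. With events spread over 20 sites, a single site may see only one case, so a central count matters more than it did in Part 1.

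Part 2 also differs in ways that do not favour dropping the rule. Entry is wider: MDI is allowed, HbA1c runs to 9.5% instead of 9.0%, and "Patients enrolling in Part 2 are NOT required to have experience with CGM". Part 1 patients use unblinded CGM throughout; in Part 2 the sponsor's CGM is blinded and worn in two periods, personal-CGM users keep their own device, and otherwise "Patients will be provided glucometers and glucometer related supplies to monitor glucose levels, if needed". Bolus insulin is cut on Day 1 in both arms (8.11). That bears on DKA, not on hypoglycemia, and it applies in Part 1 too.

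**Working it through.** The plan derives none of its pause counts, so there is no planned figure to reproduce. The check has two parts.

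**1. Text.** Study-level counts, applied separately to severe hypoglycemia and to DKA:

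| Part | Patients | Pause count | Source |
|---|---|---|---|
| Sentinels | up to 6 | 2 | Protocol 3.1.1.2 |
| Part 1 | about 30 | 3 | Protocol 3.2.1 |
| Part 2 | about 90 | none | none in Protocol 3.2.2, 9.8.2, 9.8.3, 10.9, 14; SAP 1.10, 7.7.2 |

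Scheduled contacts after Day 1, excluding follow-up:
- Part 1: 5 visits (Weeks 2, 4, 6, 8, 12) + about 6 calls in Weeks 1 and 2 + 6 later calls = about 17.
- Part 2: 4 visits (Weeks 2, 6, 10, 12) + 3 calls (Weeks 1, 4, 8) = 7.

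**2. What a Part 2 count would do.** The documents give no event rates, so every 12-week risk below is an assumption. X is the number of patients with at least one episode of one event type, pooled over arms, all followed for 12 weeks.

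*Equal risk p in both arms:* X ~ Binomial(n, p), and the pause probability is P(X ≥ k).

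| Rule | 2% | 5% | 10% |
|---|---|---|---|
| Part 1: 3 of 30 | 0.022 | 0.188 | 0.589 |
| 3 of 90 | 0.27 | 0.83 | 0.995 |
| 5 of 90 | 0.035 | 0.47 | 0.95 |
| 6 of 90 | 0.010 | 0.29 | 0.90 |
| 7 of 90 | 0.002 | 0.16 | 0.81 |

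Part 1's 3, carried unchanged to 90 patients, would pause about one trial in four at a 2% risk with no drug effect.

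*Excess risk on TTP399:* X = Binomial(45, placebo risk) + Binomial(45, TTP399 risk), by convolution. At 2% on placebo and 10% on TTP399, P(X ≥ k) is 0.64, 0.46 and 0.29 for k = 5, 6 and 7.

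*Adding an early trigger (3 of the first 30):* pause probability = 1 − Σ over x = 0, 1, 2 of P(X30 = x) · P(X60 ≤ k − 1 − x), where X60 counts the remaining 60 patients (15 + 15 in the first 30 and 30 + 30 after, for unequal risks).

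| 3 of first 30, or k of 90 | 2% both arms | 5% both arms | 2% / 10% |
|---|---|---|---|
| k = 5 | 0.048 | 0.50 | 0.66 |
| k = 6 | 0.028 | 0.36 | 0.51 |
| k = 7 | 0.023 | 0.27 | 0.40 |

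The early trigger matters for timing. At 2%/10%, once 45 patients (22 + 23) have completed, a count of 7 alone has fired with probability 0.017; with the early trigger the figure is 0.27.

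*Either event type*, if the two are independent and share the same risk: 1 − (1 − q)². With k = 7 and the early trigger, no drug effect: 1 − (1 − 0.0229)² = 0.045 at 2%, and 1 − (1 − 0.2675)² = 0.46 at 5%. Part 1's rule gives 0.043 and 0.34.

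**The case against.** The best defence is that the omission is staged design. The Sentinels were an open-label escalation and Part 1 a learning phase. The Sentinels had no severe hypoglycemia or DKA (3.4.1), Part 2 opens only if Part 1 raises no safety concern, and 10.9 considers Part 2 oversight directly. Review of each severe hypoglycemia or DKA episode starts at the first case, SAEs also reach an IRB outside the sponsor, and the exclusions closest to these harms (recent DKA, repeated severe hypoglycemia) are the same in Parts 1 and 2.

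Much of this stands. A reader might infer that Part 2 is unmonitored, or that events there would go unnoticed; the documents do not support that. Nor do they show that Part 2 patients have a higher event risk, since no rates are given. A reader might also infer that no trigger exists anywhere, but SAP 7.7.2 points to a safety review plan that was not available.

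What the defence does not explain is why a mandatory pause was kept in Part 1, which had the same monthly reviews, the same independent evaluation and the same dose, and then left out of Part 2. The documents give no reason.

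A second objection is that any particular count is arbitrary. That is fair as to the number. The choice turns on the background rate: at 2%, 5 of 90 costs little (0.035) and detects far more than 7 (0.64 against 0.29), while at 5% it would pause nearly half the time without a drug effect. This argues for the sponsor to choose and justify the count, not for having none.

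**Conclusion.** The point holds for the Protocol and SAP: neither contains a number of affected patients at which Part 2 must pause, and every safeguard that applies leaves a study-level pause to judgment. That absence is certain on the text available. The size of the benefit from a count is not, because it rests on assumed 12-week risks, independence between patients, and completed follow-up of those counted. Calendar timing depends on an enrolment rate that is not given. Even the early trigger with 7 of 90 would miss a 2%/10% excess about 60% of the time, so a count adds to case review and cannot replace it. This should be corrected: the plan as written gives weaker protection by rule in the larger, wider-entry and less often contacted part.

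**What to change.** Add a *Stopping Criteria Part 2* paragraph to Protocol 3.2.2, using the event definitions in 3.2.1 and counting patients pooled over arms, separately for severe hypoglycemia and for DKA. Pause for review if either is reached:

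- 3 or more of the first 30 Part 2 patients randomized; or
- a stated number between 5 and 7 of all Part 2 patients, chosen and justified by the sponsor from its expected background rate (toward 5 if that is near 2%, toward 7 if near 5%).

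The independent evaluator already named in 9.8.2, 9.8.3 and 10.9 keeps the count, notifies the sponsor when it is reached, may recommend a pause at any lower number, and looks by arm only after a trigger. If the safety review plan already holds a trigger, cite it in 3.2.2 instead.

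The cost is one paragraph, a cross-reference in 10.9 and a line in the evaluator's charter. The pooled count needs no unblinding. The by-arm look needs code access and a firewall from the sponsor, arranged in advance, because 10.9 leaves the endocrinologist's unblinding open. The downside is an occasional unneeded pause for review, with the probabilities shown above; it does not end the study.
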